7.3 Investigational Plan

Subjects' preoperative MRI and their history will be reviewed at the weekly CUIMC Pediatric Neuro-Oncology Tumor Board to determine disease status, and to confirm eligibility criteria and to schedule the admission date. A recent (no longer than 7 days prior to the time of the procedure) MRI with and without Gadolinium contrast that includes T1, T2, and FLAIR is required, otherwise the MRI will have to be repeated.

On the day of admission, the subject will present to the Pediatric Oncology Outpatient clinic and will be brought to the Radiation Oncology Suite (for the Navigator-Guided Focused Ultrasound (NgFUS)) (Children Hospital of New York (CHONY) Floor 3) and subsequently to the Pediatric Oncology outpatient clinic (HIP-7). Institutional policies regarding COVID for transportation will be followed.

Columbia University Irving Medical Center
Protocol Version 4.0 Date: 12.10.2021

In the radiation oncology suite, under the supervision of the Pediatric Oncology and Radiation Oncology teams, the subject will undergo:

- Focused Ultrasound and injection of DEFINITY® Microbubbles using the NgFUS system with the following ultrasonic parameters and microbubble dose:

Table I: NgFUS treatment parameters

| | |
|------------------------------------|----------------------------------------|
| FUS frequency | 0.25 MHz |
| Acoustic pressure | 200 kPa _{pk-neg} |
| Pulse length | 2,500 cycles or 10 ms |
| Pulse repetition frequency | 2 Hz |
| Total sonication time per location | 2 min |
| Definity microbubble dose | 10 µl/kg |
| Number of Tumor sites | Level A: 1 Level B: 2 Level C: 3 |

[figure not shown]
FUS will be aimed for non-enhancing peritumoral areas. Even if there is some contrast enhancement before FUS, this should be clearly increased following FUS. The focal area is quite big (6mm x 6mm x 49mm), so there should be clear opening in the neighboring non-enhancing tissue.

The total estimated time for the FUS procedure is 30-45 min.

Subjects will be sonicated, according to the pre-treatment MRI. Following the NgFUS procedure, subjects will be brought back to the Pediatric Oncology Outpatient clinic where they will receive the oral Panobinostat 15 mg/m².

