7.6 Opening and Closing of the BBB

7.6.1 Radiological Evidence of the BBB Opening

The BBB will be determined to be open if within 5mm of site of FUS, there is evidence of enhancement seen on T1 weighted post contrast images.

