7.6.2 Radiological Evidence of BBB Closure

The BBB will be determined to be closed if within 5mm of site of FUS, there is no evidence of enhancement seen on T1 weighted post contrast images.

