7.6.3 Additional MRIs to Confirm BBB Closure

The following steps will be taken if at any time any of the MRIs conducted to confirm whether the BBB is open or closed according to the definitions laid in sections [7.6.1](#) or [7.6.2](#) are unmet:

If the MRI to confirm the closure of the BBB on Day 3 does not show evidence of closure:

- subjects will no longer receive another NgFUS treatment on Day 3 to open the blood brain barrier.
- Instead, subjects will receive their scheduled Day 3 dose of Panobinostat and another MRI to confirm closure of the blood brain barrier on Day 5 prior to the scheduled FUS treatment.
- An MRI to confirm closure will be repeated every 48 hours (for a maximum of 3 times) to confirm closure in case of evidence of persistence of opening.
- If the MRI fails to show closure after 3 MRIs, Early Stopping Guidelines and Withdrawal criteria from [section 12.3](#) will be followed.
- Subjects whose BBB takes longer than anticipated to show closure will also receive an additional MRI to confirm closure in the subsequent cycle (even if not planned in the initial study schema).

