12.3 Early Stopping Guidelines

In the event 2 DLTs occur for more than 1 subject at a NOTS (number of tumor sites) level (as defined in [section 7.2](#)), study enrollment will be immediately halted. There will be at least 14 days following completion of the FUS treatment of the patient(s) on study before any subsequent patient is enrolled. After re-evaluation and consultation with the HICCC DSMC board, the trial may re-initiate enrollment with adjusted treatment parameters after a consensus is agreed upon by the Sponsor-Investigator and the HICCC DSMC, and a subsequent modification is reviewed/approved by the local PRMC/IRB. If a consensus cannot be reached, no further enrollment will be permitted on the trial and closure procedures will be initiated. In addition, the study will be discontinued at any given time if more than 20% of patients experiencing medical complications including the development of significant, irreversible deterioration during the treatment. With this rule and under the assumption of the true probability of having the medical complication is 10%, the probability of stopping the study due to the medical complication is 0.02 when the targeted total sample size is 6 and is 0.053 when the targeted total sample size is 9.

If the MRI to confirm opening of the BBB for any subject is irregular at any time during the cycles, the subject will not receive the scheduled dose treatment until a decision is made by the investigating team.

If the MRI confirm the closure of the BBB for any subject are irregular at any time, the subject will not receive any further FUS treatments and will receive another MRI to confirm closure every 48 hours for a maximum of 3 times. If the subject does not show BBB closure after 3 MRIs, the subject will come off the study. The subject will be able to receive the scheduled dose of drug, unless otherwise specified by the investigating team.

Response and progression will be evaluated in this study using the international criteria proposed by the updated Pediatric Response Assessment in Neuro-oncology (RANO) guidelines[49].

| Criterion | Complete Response | Partial Response | Stable Disease | Progressive Disease |
|----------------------------------------|---------------------|---------------------|---------------------------------|---------------------|
| T1-weighted post-Gd measurable disease | None | ≥50% decrease | <50% decrease but <25% increase | ≥25% increase |

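### The BBB closure rule (7.6.2) has no baseline term, so enhancement present before FUS that persists cannot be scored closed and takes the subject off study; the opening rule (7.6.1) has the same gap

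*Combined protocol and SAP*

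**What the plan says.** - **Definitions.** Under 7.6.1 the barrier is "open if within 5mm of site of FUS, there is evidence of enhancement seen on T1 weighted post contrast images". Under 7.6.2 it is "closed if within 5mm of site of FUS, there is no evidence of enhancement seen on T1 weighted post contrast images". Each rule scores a single scan, and neither mentions the scan taken before FUS.
- **Consequences.** 7.6.3 covers MRIs done to confirm "whether the BBB is open or closed according to the definitions laid in sections" 7.6.1 and 7.6.2. If the Day 3 scan does not show closure, "subjects will no longer receive another NgFUS treatment on Day 3 to open the blood brain barrier". The MRI is repeated every 48 hours, at most 3 times, "in case of evidence of persistence of opening". Section 12.3 adds: "If the subject does not show BBB closure after 3 MRIs, the subject will come off the study".
- **Choice of site.** 7.3 states: "FUS will be aimed for non-enhancing peritumoral areas". It then allows that a target may already enhance, and in that case expects a definite rise after FUS. Section 10 prefers a peripheral site that does not enhance on the pre-treatment MRI, but only as a preference. The eligibility criteria (8.1) do not require such a site.
- **Use of the opening call.** 10.1 sets success at safe opening in at least 75% of cases. It compares each patient's opening scan with the scan before, and it sizes the comparison on an after-minus-before difference. Section 10 says the 7.6 evidence will be recorded as well. Under 12.6, failure to open the barrier in 3 subjects prompts contact with the FDA about the ultrasound settings; how opening is judged is not stated.
- **Tumour enhancement.** The response table in 12.3 follows "T1-weighted post-Gd measurable disease". So the plan allows for enhancing tumour, although the table says nothing about the FUS sites.

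**The concern.** A closure test should ask whether the opening made by FUS has gone. As written, 7.6.2 asks whether the site shows any enhancement at all. The two questions agree only when nothing enhanced there beforehand. Where something did, a child can lose FUS sessions, have extra gadolinium scans and leave the study because of tumour enhancement that FUS did not cause. That child still gives safety data at the levels already treated, since the DLT period starts on the first FUS day (12.2), but gives none at the higher levels. In a trial of at most 15 subjects, each such loss thins the information on 2 and 3 sites.

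The opening rule errs the other way. A site that enhanced before FUS is scored open even if FUS did nothing.

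**Working it through.** **1. The plan's own figure.** 10.1 gives a difference of 72 mm³, SD 50 mm³, alpha 0.05, power 0.80, paired t-test, at least 6 subjects. With d = 72/50 = 1.44 and a two-sided test, noncentral-t power is 0.677 at n = 5 and 0.803 at n = 6. The stated 6 reproduces. It already rests on an after-minus-before difference, so reading opening against a reference scan leaves it unchanged.

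**2. The rules case by case.**

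| Before FUS | What FUS did | Day 1, 7.6.1 | Day 1, against reference | Day 3, 7.6.2 | Day 3, against reference |
|---|---|---|---|---|---|
| No enhancement | Opened, then closed | open | open | closed | closed |
| No enhancement | Opened, still open | open | open | not closed | not closed |
| Enhancement that persists | Opened, then closed | open | open | **not closed** | closed |
| Enhancement that persists | Did not open | **open** | not open | **not closed** | closed |

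The readings differ only in the last two rows, the situation that 7.3 foresees. No section exempts enhancement already present.

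**3. Cost when closure fails for this reason.**
- Scans: Day 3, then every 48 hours. If the limit means 3 scans in all, they fall on Days 3, 5 and 7 (2 unplanned). If it means 3 repeats, the repeats fall on Days 5, 7 and 9 (3 unplanned).
- Sessions: 6 cycles × 2 weeks × 3 days = 36. Planned closure scans are in Cycles 1, 3 and 5 (7.5), before the Day 3 session. Sessions received by then: Cycle 1, 1; Cycle 3, 12 + 1 = 13; Cycle 5, 24 + 1 = 25. If FUS is given in Week 1 only, they are 1, 7 and 13 of 18.
- Levels: failure in Cycle 1 leaves nothing at Levels B and C. Failure in Cycle 3 leaves one session at Level B and none at C.

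**4. Opening, if 7.6.1 is applied literally.** Assumptions, not in the documents: one call per subject; true opening rate 60%; a share q of sites enhances before FUS, independently of whether FUS opens them; safety is ignored. Scored rate = q + (1 − q) × 0.60. The 75% mark needs 5 of 6 or 12 of 15 (binomial).

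| q | Scored rate | P(at least 5 of 6) | P(at least 12 of 15) |
|---|---|---|---|
| 0 | 0.60 | 0.23 | 0.09 |
| 0.10 | 0.64 | 0.30 | 0.15 |
| 0.25 | 0.70 | 0.42 | 0.30 |
| 0.50 | 0.80 | 0.66 | 0.65 |

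At q = 0 there is no effect. For 12.6, each subject wrongly scored open delays the trigger by one true failure.

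**5. Age of the reference scan under the fix.** Two-week cycles with a one-week gap start on study days 1, 22, 43, 64, 85 and 106. Planned closure scans fall on days 3, 45 and 87. The latest earlier closure scan is then 22 − 3 = 19, 64 − 45 = 19 and 106 − 87 = 19 days old on Day 1 of Cycles 2, 4 and 6. It is 43 − 3 = 40 and 85 − 45 = 40 days old on Day 1 of Cycles 3 and 5, and 42 days old when closure is judged on Day 3 of those cycles. The checkpoint MRIs in between are without contrast (7.2, 7.5), so they cannot serve.

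**The case against.** The strongest reply is that site selection handles the problem. FUS is aimed at non-enhancing tissue, a contrast MRI at most 7 days old is mandatory, and for such sites no enhancement is the same as return to baseline. This stands as a limit on how often the gap matters. It does not close the gap, because the choice of site is an aim and 7.3 itself provides for the exception.

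Second, the strict rule fails safe: it withholds re-sonication wherever opening cannot be excluded, panobinostat may continue, and a certified radiologist reads the scans (13.2). This also stands, and the fix must keep that caution.

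Third, the mention of persisting opening in 7.6.3 suggests a FUS-related reading. But 7.6.3 ties its steps to the 7.6.1 and 7.6.2 definitions, under which any enhancement is open.

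Fourth, the before/after reading is the natural one for the 75% criterion, because 10.1 places the comparison beside it, and 12.6 only prompts a discussion of settings. That is fair. The inflation in step 4 arises only if someone applies 7.6.1 literally, but Section 10 points readers to 7.6 and no section says which reading prevails.

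**Conclusion.** The point holds. Given enhancement before FUS that persists, the text of 7.6.2, 7.6.3 and 12.3 leads to withdrawal. Given the same enhancement, 7.6.1 scores opening whatever FUS did, against 7.3 and the comparison in 10.1. The size per affected subject is as in step 3. The frequency is unknown and may be zero. The definitions should be fixed, but the design is not called into question.

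A reader might infer more than the documents support:
- **A share of subjects who would be lost.** No rate of pre-FUS enhancement is given. Nor is it stated whether sites carry over between levels (3 separate windows per subject) or are chosen afresh (1 + 2 + 3 = 6), so no bound can be set.
- **That the 5 mm window takes in much tissue outside the focus.** This depends on whether the FUS site means the target point or the whole focal volume, which 7.6 does not say.
- **That 10.2 gives a rival definition of opening.** It specifies a paired test of enhancement and does not define opening.
- **That the closure rule exposes children to unsafe re-sonication.** Its error is in the cautious direction.

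**What to change.** - **7.6.1:** open means new or clearly increased enhancement within 5 mm of the FUS site against the reference scan.
- **7.6.2:** closed means no enhancement in that window beyond what the reference scan shows. If the reader cannot tell, score not closed.
- **Reference scan:** the screening contrast MRI for Cycle 1; after that, the latest earlier contrast scan that showed closure. A closure scan is never its own reference.
- **Scope:** state that these definitions govern the 75% criterion in 10.1 and the 3-subject trigger in 12.6. Keep every action in 7.6.3 and 12.3 for enhancement above the reference.

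The cost is wording and a side-by-side read of scans already planned. The reported opening rate may be lower. With a reference 40 to 42 days old in Cycles 3 and 5, tumour growth in the window may be read as opening or as non-closure. Non-closure is the cautious error, and 9.1 ends the treatment period on progression, but the protocol should state this as a limitation.

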7.6.3 Additional MRIs to Confirm BBB Closure

The following steps will be taken if at any time any of the MRIs conducted to confirm whether the BBB is open or closed according to the definitions laid in sections [7.6.1](#) or [7.6.2](#) are unmet:

If the MRI to confirm the closure of the BBB on Day 3 does not show evidence of closure:

- subjects will no longer receive another NgFUS treatment on Day 3 to open the blood brain barrier.
- Instead, subjects will receive their scheduled Day 3 dose of Panobinostat and another MRI to confirm closure of the blood brain barrier on Day 5 prior to the scheduled FUS treatment.
- An MRI to confirm closure will be repeated every 48 hours (for a maximum of 3 times) to confirm closure in case of evidence of persistence of opening.
- If the MRI fails to show closure after 3 MRIs, Early Stopping Guidelines and Withdrawal criteria from [section 12.3](#) will be followed.
- Subjects whose BBB takes longer than anticipated to show closure will also receive an additional MRI to confirm closure in the subsequent cycle (even if not planned in the initial study schema).

8. STUDY POPULATION

8.1 Eligibility

8.1.1 Diagnostic Criteria

- Ages 4-21 years.
- Subjects' with evidence of clinical and/or radiographic progression of Diffuse Midline Glioma
- Radiological diagnosis of DMG with tumor involving the pons (intrinsic, pontine based infiltrative lesion; hypointense in T1 weighted images (T1WIs) and hyperintense in T2 sequences, with mass effect on the adjacent structures and occupying at least 50% of the pons), thalami and/or histological confirmation of H3K27M mutation confirmation of pontine or thalamic glioma.

8.1.2 Subject Characteristics

Subjects must be healthy enough to tolerate FUS and MRI and any anesthesia necessary based on the opinion of the principal investigator. Subjects must also be able to swallow capsules (for Panobinostat dosing). Other criteria include, but is not limited to:

Prior therapy:

- Patients must have fully recovered from the acute toxic effects of all prior anti-cancer therapy and must meet the following minimum duration from prior anti-cancer directed therapy prior to enrollment.
 - Cytotoxic chemotherapy or anti-cancer agents known to be myelosuppressive: At least 21 days after the last dose of cytotoxic or myelosuppressive chemotherapy.
 - Anti-cancer agents not known to be myelosuppressive: At least 7 days must have elapsed from last dose of agent.
 - Antibodies: At least 21 days must have elapsed from infusion of last dose of antibody.
 - Interleukins, Interferons, and Cytokines: At least 21 days must have elapsed since the completion of interleukins, interferon, or cytokines.

- Stem cell infusions: At least 42 days must have elapsed after completion of an autologous stem cell infusion, and at least 84 days must have elapsed after completion of an allogeneic stem cell infusion.
- Cellular therapy: At least 42 days must have elapsed since the completion of any type of cellular therapy
- Radiotherapy (XRT): At least 1 month must have elapsed after local XRT.
- Subjects must be on a stable or decreasing dose of steroids, as well as stable dose of anti-seizure medication for 1 week.

Performance status:

- Karnofsky performance status or Lansky play score of ≥ 70

Hepatic:

- Total bilirubin: within normal institutional limits
- AST(SGOT)/ALT(SGPT): $\leq 2.5 \times$ institutional upper limit of normal

Renal:

- Creatinine: within normal institutional limits
- Creatinine clearance: $\geq 60 \text{ mL/min}/1.73\text{m}^2$ for subjects with creatinine levels above institutional normal

Hematopoietic:

- Absolute neutrophil count: $\geq 1,500/\mu\text{L}$
- Platelet count: $\geq 100,000/\mu\text{L}$
- Hemoglobin level: $\geq 10\text{g/dL}$
- PT and APTT: within normal institutional limits
- No documented current bleeding disorder

Other:

- Not pregnant or nursing – negative serum pregnancy test, if of childbearing potential, within 7 days of study entry
- Subjects with a history of seizures/epilepsy should be on anti-convulsant medication prior to the first operative procedure on study.
- Subjects must undergo a baseline EKG within 7 days of study enrollment.
- Subjects must be able to undergo MR imaging with gadolinium-based contrast administration (e.g. no ferrous-containing implants, no pacemakers, etc.)
- All subjects or their legal guardians must sign a document of informed consent indicating their understanding of the investigational nature and the potential risks associated with this study. When appropriate, pediatric subjects will be included in all discussions in order to obtain verbal and written assent

8.1.3 Exclusion Criteria

- Subjects with spinal DMGs.
- Subjects with a medical condition that would preclude general anesthesia
- Subjects with evidence of any active infection
- Subjects with documented allergy to compounds of similar chemical or biologic composition to Panobinostat or gadolinium compounds
- Subjects with evidence of tumor hemorrhage

- Subjects with an uncorrectable bleeding disorder
- Subjects with signs of impending herniation or an acute intratumoral hemorrhage
- Subjects with systemic diseases which may be associated with unacceptable anesthetic/operative risk
- Subjects with implanted electrical devices, metallic implants
- Subjects with uncontrollable hypertension
- Subjects with a history of stroke or cardiovascular disease
- Subjects with cerebrovascular diseases
- Subjects with coagulopathy or under anticoagulant therapy.
- Pregnant or breast-feeding women will not be entered on this study, since there is yet no available information regarding human fetal or teratogenic toxicities. A pregnancy test must be obtained in girls who are post-menarchal. Males with female partners of reproductive potential or females of reproductive potential may not participate unless they have agreed to use two effective methods of birth control- including a medically accepted barrier method of contraception (e.g., a male or female condom) for the entire period in which they are receiving protocol therapy and for at least 1 week following their last study treatment requirement. Abstinence is an acceptable method of birth control.

9. FOLLOW-UP

9.1 Duration of Therapy and Follow-up

The treatment period of this study begins at the time of the NgFUS ultrasound and concludes upon evidence of progression . Patients will be monitored for AEs and SAEs for up to 90 days post completion of study. During follow-up the study team will be responsible for conducting a physical exam, repeating MRI (if indicated by the primary physician), and collecting survival data.

10. MEASUREMENT OF EFFECT

The MRIs should include volumetric sag T1 pre- and post- contrast images with reconstructions as well as dynamic contrast enhanced images (which will be acquired over a 30 minute period to allow for sufficient time for the contrast to cross the blood brain barrier site which was opened with FUS), axial post contrast SE T1 as well as sag T2 volumetric (with coronal and axial reconstructions) (can be acquired post-contrast), axial T2 FSE (can be acquired post-contrast), axial SWAN, axial FLAIR (must be acquired pre-contrast), and axial DWI (must be acquired pre-contrast). Initially, we will ideally choose the area for opening of the blood brain barrier with NgFUS at a peripheral site of the tumor, which does not demonstrate post contrast enhancement on the pre-treatment MRI. We will choose one site for blood brain barrier opening. We can measure contrast enhancement as described in Mainprize et al as well as has previously been measured by members of our group in past work (by investigators [name] and [name]). Radiological evidence of successful BBB opening and closing will also be noted as mentioned in [section 7.6.](#)

10.1 Sample Size Determination

A minimum of 3 and maximum of 15 patients will be recruited in the study. The minimum number of subjects is to account for “dose” limiting toxicities disallowing more subjects to be enrolled. As this is a feasibility study, the power and sample size is not justified. However, successful methodology will be concluded if the BBB opening is safely opened in at least 75% of the cases as evidenced on MRI. The scan with the BBB opening will be compared to the scan before BBB opening for each patient. Power analysis shows that for a detectable difference of 72 mm^3 (after BBB opening - before BBB opening) and a standard deviation of 50 mm^3 , at least 6 subjects are needed to report a result at the level of $\alpha=0.05$ and Power=0.80 with paired student's t-test.

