COLUMBIA UNIVERSITY
MEDICAL CENTER

**A Feasibility Study Examining the Use of Non-Invasive Focused Ultrasound (FUS)
with oral Panobinostat Administration in Children with Progressive Diffuse
Midline Glioma (DMG)**

Short Title: FUS Panobinostat for DMG
Columbia University Irving Medical Center

KEY TRIALS CONTACTS:

PRINCIPAL INVESTIGATOR:

[name]., Ph.D.

[name]
[name]
T: [contact]
[name]
[contact]

CO-INVESTIGATORS:

[name].

[name]
T: [contact]
[contact]

[name].

[name]
[name]
[name]
T: [contact]
[contact]

[name]., Ph.D.

[name]
[name]
T: [contact]
[contact]

[name].

[name]
[name]
T: [contact]
[contact]

[name]., Ph.D.

[name]
[name]
T: [contact]
[contact]

[name].

[name]
[name]
T: [contact]
[contact]

[figure not shown]
STATISTICIAN:

[name].

[name]
[name]
T: [name]
[contact]

| | | |
|-----------------------------------------------------------|--------------------------------------------------------------------------------------------------------------------------------------------------------------------------------------|--------------------------------------------------------------------------|
| Trial Title | Feasibility Study Examining the use of Non-Invasive Focused Ultrasound (FUS) with oral Panobinostat Administration in Children with progressive Diffuse Midline Glioma (DMG). | |
| Short Title | FUS Panobinostat for DMG | |
| Trial Design | Prospective non-randomized single arm feasibility study | |
| Trial Participants | Children | |
| Planned Sample Size | Maximum 15 subjects | |
| Treatment duration | 6 months | |
| Follow-up duration | 2 years | |
| Investigational Medical Device: Focused Ultrasound | | |
| | Objectives | Outcome measures |
| Primary Endpoint | To evaluate the safety and feasibility of using FUS to open one, two or three tumor sites for administration of Panobinostat in children with progressive DMG | Physical exam, laboratory studies, |
| Secondary Endpoints | To determine blood brain barrier/tumor imaging changes using FUS in children with progressive DMG | Documenting changes in the pattern of contrast enhancement on MRI |

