7. STUDY DESIGN

7.1 General Design

The purpose of this study is to evaluate the feasibility of opening the BBB safely using specific parameters of focused ultrasound in progressive/recurrent diffuse midline gliomas in one, two or three tumor sites and receive Oral Panobinostat 15 mg/m². The study will consist of a minimum of 3 to a maximum of 15 subjects. See [section 7.3](#) for a treatment schema.

The clinical neuronavigator will be identical to the NHP study with the difference of human module in the software used, as well as employing a separate set of navigation tools that are used for human subjects only.

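### Section 10.1 concludes success from a bare 75% of undefined 'cases' at an unfixed N between 3 and 15, so a very small sample can pass and the rule has no defined error rate

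*Combined protocol and SAP*

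**What the plan says.** The number of subjects appears in several places.

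- The synopsis, in the row for planned sample size, gives a ceiling: "Maximum 15 subjects".
- Section 7.1 gives a range: "The study will consist of a minimum of 3 to a maximum of 15 subjects".
- Section 10.1 repeats it: "A minimum of 3 and maximum of 15 patients will be recruited in the study". It explains the minimum by dose-"limiting toxicities disallowing more subjects to be enrolled".
- Section 10.1 also reports a paired t-test calculation under which "at least 6 subjects are needed to report a result".
- Section 12.3 gives the chance of stopping for medical complications, which "is 0.02 when the targeted total sample size is 6 and is 0.053 when the targeted total sample size is 9".

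On justification, section 10.1 is open: "As this is a feasibility study, the power and sample size is not justified". The next sentence nevertheless sets a decision rule: "successful methodology will be concluded if the BBB opening is safely opened in at least 75% of the cases as evidenced on MRI". Section 10.2 calls the analysis descriptive and plans medians, ranges, proportions and a Wilcoxon signed-rank test, but no confidence interval. Section 7.5 schedules an MRI to determine opening on Week 1 Day 1 of every cycle, so up to six per subject. Section 7.2 has one, two or three tumor sites sonicated, depending on the level.

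**The concern.** A descriptive study needs no error rate. A rule under which success will be concluded is different, because how often it passes when the technique works poorly depends on the denominator, the unit counted and the moment of reading. None of the three is fixed. The 3 and 15 are accrual limits, the 6 in section 10.1 belongs to the enhancement-volume comparison, and the 6 and 9 in section 12.3 belong to a safety rule. No number is attached to the 75% criterion.

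This is the only success criterion the plan states. Met at three or four subjects, it would let the report call the methodology successful on data compatible with an opening rate well below one half.

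**Working it through.** **The plan's own figures.** Section 10.1: standardised difference d = 72/50 = 1.44, taking 50 mm³ as the SD of the paired difference and a two-sided 5% test. Exact noncentral-t power is 0.677 at n=5 and 0.803 at n=6, so the stated 6 reproduces. It concerns mean enhancement volume and says nothing about a proportion of openings.

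Section 12.3: with a 10% complication rate, P(X ≥ 3) is 0.0159 at n=6 and 0.0530 at n=9, matching the stated 0.02 and 0.053. No value is given for 15.

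**The 75% rule, taking one case as one subject.** The smallest passing count is r = ⌈0.75N⌉. With true opening rate p,

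P(pass) = Σ from k=r to N of C(N,k) pᵏ(1−p)ᴺ⁻ᵏ.

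The documents give no unacceptable or target opening rate, so every p here is an assumption. At p = 0.5:

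- N=3, r=3: 1/8 = 0.125
- N=4, r=3: (4+1)/16 = 0.3125
- N=6, r=5: (6+1)/64 = 0.109
- N=9, r=7: (36+9+1)/512 = 0.090
- N=15, r=12: (455+105+15+1)/32768 = 0.018

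Across a range of true rates, with the Clopper-Pearson interval at the minimum passing result:

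| N | Minimum pass | Exact 95% CI | p=0.5 | p=0.6 | p=0.75 | p=0.9 |
|---|---|---|---|---|---|---|
| 3 | 3/3 | 29-100% | 0.125 | 0.216 | 0.422 | 0.729 |
| 4 | 3/4 | 19-99% | 0.312 | 0.475 | 0.738 | 0.948 |
| 6 | 5/6 | 36-99.6% | 0.109 | 0.233 | 0.534 | 0.886 |
| 9 | 7/9 | 40-97% | 0.090 | 0.232 | 0.601 | 0.947 |
| 15 | 12/15 | 52-96% | 0.018 | 0.091 | 0.461 | 0.944 |

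At p = 0.5 the ratio between the plan's minimum and maximum N is 0.125/0.0176 ≈ 7. Between N=4 and N=15 it is 0.3125/0.0176 ≈ 18. The jump at N=4 arises because 75% is met exactly there. Of the five sizes shown, only N=15 has a minimum passing result whose interval excludes 50%.

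**The unit.** If a case were an opening scan, four subjects could supply up to 4 × 6 = 24 correlated observations, more if sites are counted, and none of these binomial figures would apply. The text does not settle which is meant.

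**The case against.** The strongest defence has four parts.

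*The plan claims little.* It disclaims a sample-size justification and calls the analysis descriptive, and under a toxicity-driven escalation the final N cannot be wholly fixed. That stands against demanding a powered design. It does not excuse a pass/fail conclusion without a denominator.

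*The numbers do not contradict each other.* Three and 15 are limits, 6 is a floor for another analysis, and 6 and 9 are conditional illustrations inside the range. Largely true; what remains is that section 12.3 calls 6 and 9 targeted totals when no target is named anywhere. The spread is also modest at 3, 6 and 9 (0.125, 0.11, 0.09). The large differences come from N=4, which the documents permit but never mention, and N=15.

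*'Safely' limits small-sample success.* Low accrual is tied to toxicity. If a subject with a dose-limiting toxicity counts as not safely opened, a halt after such events in two subjects leaves at most 1/3, 2/4 or 4/6, all below 75%. This has force, but section 10.1 does not define the word, and termination after a single serious procedure-related event under section 12.6 could still leave 3/4. The calculations above count openings only.

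*No one plans to stop on good results.* A reader might infer that, because opening scans are read as the open trial proceeds, accrual can end on a favourable run. The documents do not support this. The only stated reasons for ending accrual early concern safety, the minimum of 3 is attributed to toxicity, and the provision for failed opening in three subjects in section 12.6 leads to a discussion of parameters with the regulator. Silence about other reasons for stopping between 3 and 15 is not a success stop, so optional-stopping error rates should not be attributed to this plan.

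**Conclusion.** The concern holds as a defect in the decision rule. As written, and with a case read as a subject, 3/3 or 3/4 concludes success although the exact intervals reach down to 29% and 19%. The chance of passing at a true rate of 50% runs from 0.31 at N=4 to 0.018 at N=15. These sizes rest on three assumptions: a case is one subject, openings are independent with a common rate, and 'safely' removes no openings from the count. The 50% rate is illustrative.

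The consequence is an unsound conclusion from a small sample, not a risk to subjects. It deserves correction because it affects the plan's only success criterion and the correction is cheap.

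**What to change.** In section 10.1:

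1. Name one planned N. The existing maximum of 15 needs no additional patients.
2. Define a case as one subject, for example by the first opening MRI in Cycle 1, and state what counts as safely opened.
3. Read the 75% rule once, at the end of accrual, and report the exact Clopper-Pearson 95% CI beside the proportion.
4. If accrual ends below the planned N, report the proportion and exact CI as the result and do not rest a success conclusion on the point estimate alone. A strong short series is not discarded: 14/14 would carry a lower limit of 0.025^(1/14) = 0.77, which speaks for itself.

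In section 12.3, give the stopping probability at the same N and state the event count used. At N=15 and a 10% complication rate, more than 20% means four or more subjects, and P(X ≥ 4) = 0.056 for a single reading at the end. The count matters because the quoted 0.02 and 0.053 correspond to three or more events, while two of 6 (33%) or two of 9 (22%) already exceeds 20%. That is a separate discrepancy, to be reconciled by the sponsor.

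Cost: wording in two sections, with no change to treatment. The sponsor gives up point-estimate success claims at small N. At N=15 with 12 or more required, a true opening rate of exactly 75% passes only 46% of the time, against 94% at a true rate of 90%. The sponsor should accept that knowingly before the data are read.
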